2.2 Secondary Objectives

- 2.2.1 To monitor adverse events/toxicity every 4 weeks while on treatment
- 2.2.2 To evaluate change in phenolic levels (total and component, blood and urine) from baseline to 4 and 8 weeks on MGE
- 2.2.3 To evaluate change in serum cytokines and growth factors from baseline to 4 and 8 weeks on MGE
- 2.2.4 To observe the response rate of MGE in patients with metastatic cancer.
- 2.2.5 To assess overall and progression-free survival in patients with metastatic cancer receiving MGE.
- 2.2.6 To assess global quality of life (FACT-G) and fatigue (PROMIS-fatigue short form) in cancer patients taking MGE.
- 2.2.7 To assess adherence to MGE treatment.

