5.2 Secondary Outcomes

- 5.2.1 Adverse events/toxicity at weeks 4, 8 and every 4 weeks thereafter if remain on treatment
- 5.2.2 Identification of measured phenolic levels (total and component phenolics) at baseline,4, and 8 weeks
- 5.2.3 Evaluate change in systemic cytokines, growth factors from baseline to 4 and 8 weeks including but not limited to: TNF α , IL6, IL6R, IL8, IL1 α , IL1 β , IGF-1, VEGF
- 5.2.4 Overall response rate (CR, PR, and SD) at 8 weeks.
- 5.2.5 PFS and OS in patients with metastatic cancer receiving MGE under the proposed regimen.
- 5.2.6 Quality of life in cancer patients taking MGE using the Functional Assessment of Cancer Therapy–General (FACT-G) measure and fatigue, as measured by the PROMIS Fatigue-Short Form.
- 5.2.7 Adherence to MGE treatment, as assessed by patient-reported medication logs and pill count every 4 weeks while on treatment.

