6.3.2 Follow-up Assessments

- 6.3.2.1 Study coordinator will contact participants 2 weeks after each clinic visit until week 8 to assess medication adherence and ascertain any potential adverse events.
- 6.3.2.2 The RN will review AE with the patient at each follow-up visit in clinic, perform pill count, obtain clinical information per protocol and administer surveys at 4 and 8 weeks per protocol. RN will obtain study labs are each visit and provide 30-day supply of MGE at prescribed dose level.

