10.0 Laboratory Studies

10.1 Phenolic assays

Total and component phenolics will be measured from blood and urine at baseline, 4 weeks, and 8 weeks if the patient remains on MGE. Blood assays will require approximately 10ml of blood. For the polyphenolic analysis²⁶ one tube of blood at each time point will be collected in tubes containing EDTA and ascorbic acid and stored at - 80°C for an indefinite period of time. The blood sample will be thawed on ice and used to measure polyphenols by ultra-high performance liquid chromatography (UPLC) coupled to mass spectroscopy detection (UPLC-MS).

A spot urine collection will be collected at baseline, 4 weeks, and 8 weeks if the patient remains on treatment with MGE. The urine will be collected into a urine collection cup and mixed with ascorbic acid; 20 mL aliquots will be stored at -80°C for an indefinite period of time. The urine will be thawed on ice and used to measure polyphenols by UPLC-MS.

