12.2 Analysis of Secondary Objective

12.2.1 To monitor toxicity at 4, 8, and every 4 weeks thereafter on MGE

To analyze objective 2.1.1, we will summarize any expected toxicities, any laboratory based toxicities, and any grade 3 or higher gastrointestinal toxicities and any grade 4 or higher toxicities using frequency tables overall and by week.

12.2.2 To evaluate change in phenolic levels (total and component, blood and urine) from baseline to 4 and 8 weeks

To analyze objective 2.2.2, we will fit a mixed model ANOVA model with phenolic level as the outcome and time (baseline, 4, and 8 weeks) as a fixed effect and subject as a random effect. We will use contrasts to estimate the changes from baseline to week 4 and week 8.

12.2.3 To evaluate change in serum cytokines and growth factors from baseline to 4 and 8 weeks on MGE

To analyze objective 2.2.3, we will fit a mixed model ANOVA model with the outcome of interest (cytokine or growth factor) as the outcome and time (baseline, 4, and 8 weeks) as a fixed effect and subject as a random effect.

We will use contrasts to estimate the changes from baseline to week 4 and week 8.

12.2.4 To observe the response rate of MGE in patients with metastatic cancer.

To analyze objective 2.2.4, we will characterize response at 8 weeks using frequency table. We will also characterize the best response at the end of treatment with MGE using a frequency table.

12.2.5 To assess overall and progression-free survival in patients with metastatic cancer receiving MGE.

To analyze objective 2.2.5, we will summarize overall survival and progression-free survival using the Kaplan-Meier method. We will calculate median survival rates and associated 95% confidence intervals. Patients will be censored at date of last contact.

12.2.6 To assess global quality of life and fatigue in cancer patients taking MGE.

Quality of Life and fatigue will be monitored every 4 weeks until the end of the study. To analyze objective 2.2.6, we will fit a mixed model ANOVA model with phenolic level as the outcome and time (baseline, every 4 weeks) as a fixed effect and subject as a random effect. We will use contrasts to estimate the changes from baseline to each follow-up time period.

12.2.7 To assess adherence to MGE treatment.

To analyze objective 2.2.7, we will summarize the percent of pills taken at the end of every 4 week period i using the formula:

Percent of pills taken_i =

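### The quality-of-life and fatigue analysis names phenolic level as its outcome, so objective 2.2.6 has no stated analysis of FACT-G or PROMIS-Fatigue

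*Combined protocol and SAP*

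**What the plan says.** Section 2.2 states objective 2.2.6 as "To assess global quality of life (FACT-G) and fatigue (PROMIS-fatigue short form) in cancer patients taking MGE". Section 5.2.6 lists the matching outcomes: quality of life by FACT-G, and "fatigue, as measured by the PROMIS Fatigue-Short Form".

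Section 12.2.6 is headed as the analysis of quality of life and fatigue. It opens with a statement about collection: "Quality of Life and fatigue will be monitored every 4 weeks until the end of the study". It then gives the model: "To analyze objective 2.2.6, we will fit a mixed model ANOVA model with phenolic level as the outcome", with "time (baseline, every 4 weeks) as a fixed effect and subject as a random effect", and contrasts from baseline to each follow-up.

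Section 12.2.2, on the phenolic objective, reads: "To analyze objective 2.2.2, we will fit a mixed model ANOVA model with phenolic level as the outcome".

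On phenolic sampling, Section 10.1 says: "Total and component phenolics will be measured from blood and urine at baseline, 4 weeks, and 8 weeks", the later samples depending on the patient still taking MGE.

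On the questionnaires, the activity table in Section 6.1 and the data collection table that goes with Section 11.0 both have them at baseline and at each four-weekly or monthly visit. Section 6.3.2.2 instead has the research nurse "administer surveys at 4 and 8 weeks per protocol".

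**The concern.** The dependent variable in the model for objective 2.2.6 is a laboratory measurement that belongs to objective 2.2.2. If 12.2.6 is followed as written, the trial repeats an analysis it already has and produces no estimate of change in quality of life or fatigue.

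Two things are at stake. First, Section 1.0 puts forward lower symptom burden, fatigue in particular, as a way MGE might help patients, so this secondary objective bears on the rationale for the product. Patients are also asked to complete the questionnaires at every monthly visit, and those data should have a stated use.

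Second, whoever corrects the outcome at analysis has to choose it: FACT-G total or a subscale, PROMIS-Fatigue raw score or T-score. With one treatment per patient and no control group, patient-reported outcomes are easily reported selectively. A choice made once the data are in hand is not pre-specified.

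A smaller point is that Section 6.3.2.2 does not agree with the questionnaire schedule given elsewhere. The corrected model needs an agreed set of time points.

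**Working it through.** No formula applies, and the plan gives no figure for this objective to reproduce. The check compares sections.

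**Step 1: objective against model outcome.**

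| Objective | Measure named in Sections 2.2 and 5.2 | Outcome named in Section 12.2 |
|---|---|---|
| 2.2.2 | Phenolics, blood and urine | Phenolic level |
| 2.2.3 | Cytokines and growth factors | Cytokine or growth factor |
| 2.2.6 | FACT-G, PROMIS-Fatigue | Phenolic level |

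The outcome matches the objective in the first two rows and not in the third. The sentence in 12.2.6 is complete and grammatical, so neither redaction nor text extraction explains the mismatch.

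**Step 2: is there another analysis of the questionnaires?** Sections 6.1, 6.3.1, 6.3.2 and the data collection table cover only when and by whom the questionnaires are given. The opening sentence of 12.2.6 also describes collection. Section 12.2 mentions neither instrument by name. Appendices F and G are listed as the instruments and are held as separate attachments. Instruments with a stated analysis: 0 of 2.

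**Step 3: what the stated model would yield.** The time factor of 12.2.6 is set against the data each variable would have.

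| Time level in 12.2.6 | Phenolics (6.1, 10.1) | Questionnaires (6.1, data collection table) | Surveys as worded in 6.3 |
|---|---|---|---|
| Baseline | Yes | Yes | Yes (6.3.1.3) |
| Week 4 | Yes | Yes | Yes (6.3.2.2) |
| Week 8 | Yes | Yes | Yes (6.3.2.2) |
| Every 4 weeks after week 8 | No | Yes | Not mentioned |

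Three results follow.

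- With phenolic level as outcome, a model can be run on baseline, week 4 and week 8 only. Its two contrasts (baseline to week 4, baseline to week 8) are those already specified in 12.2.2.
- Every contrast after week 8 is non-estimable for that outcome, so the model with its full time factor cannot be carried out.
- The four-weekly time factor fits the questionnaires and not the phenolic samples. This is good evidence that questionnaire scores were meant and that the outcome was carried over from 12.2.2.

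**Step 4: effect of the wording in 6.3.2.2.** If a nurse worked from that paragraph alone and stopped surveys at week 8, the later contrasts would also be lost for the corrected outcomes. If the schedule table is followed, nothing is lost.

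**The case against.** The strongest reply is that this is an obvious slip with little practical effect. The heading of 12.2.6, its opening sentence, its link to objective 2.2.6 and its four-weekly time factor all point to the questionnaires. The model type, time effect, random effect and contrasts are stated, and only the outcome is wrong. A statistician would probably put it right unprompted. The objective speaks of global quality of life, which suggests an overall FACT-G score. No hypothesis test, error rate or decision rule depends on the result, in a trial of 2 to 30 patients whose primary question is toxicity.

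Much of this stands. The intent is clear, and the consequence of having no estimate applies only to a literal reading. It is also fair that a phenolic model could be run on three time points, so what fails is the set of later contrasts and not the whole fit. Section 6.3.2.2 is a soft inconsistency too. It does not say that surveys stop at week 8, and its closing reference to the protocol can be read as deferring to the schedule.

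What does not fall away is that the wrong outcome stands in the operative statistical section and nothing elsewhere corrects it. A reader can infer that questionnaire scores were meant, but the text only hints at the FACT-G score and does not settle how PROMIS-Fatigue is scored. The separate appendices may give scoring rules, but they are not available here, and a scoring rule would not by itself name the analysis outcome.

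**Conclusion.** The concern holds. As written, 0 of the 2 instruments in objective 2.2.6 is analysed, the stated model duplicates 12.2.2 through week 8, and every later contrast has no data behind it. The conclusion rests on the text alone and on no assumption about sample size, variance or effect size. The loss of questionnaire data after week 8 is conditional: it occurs only if 6.3.2.2 is followed in preference to the schedule table.

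The point should be corrected, but its reach is limited. It concerns one of seven secondary objectives and leaves dose-limiting toxicity, dose escalation, the maximum tolerated dose and the sample size untouched.

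**What to change.** In Section 12.2.6, replace phenolic level with two outcomes, each in its own mixed model: the FACT-G total score and the PROMIS-Fatigue Short Form score. Keep the stated terms, with time (baseline and every four weeks) as the fixed effect and subject as the random effect, and keep the contrasts from baseline. State in the same sentence whether PROMIS-Fatigue is analysed as a raw score or a T-score. If FACT-G subscales will be reported, say that they are additional to the total.

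In Section 6.3.2.2, align the timing of the surveys with the four-weekly schedule in Section 6.1, the data collection table and 12.2.6.

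The cost is about one sentence in each section. No new data, visits or procedures are needed. The change should be made before the questionnaire data are analysed, so that the choice of score counts as pre-specified.

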6.0 Treatment Plan

6.1 Study-Related Activities

Measures / Forms	Pre- Study ^a	Baseline	Week 2 ^h	Week 4 ^j	Week 8 ^k	Every 4 weeks ^k	Off-study
Informed consent	Х						
Demographics	Х						
Medical history	Х			Х	Х	Х	
Concurrent meds	Х			Х	Х	Х	
Physical exam	Х			Х	Х	Х	
Vital signs	Х			Х	Х	Х	
Weight		Х					
Height		Х					
ECOG Performance Status	Х			Х	Х	Х	
Pill Diary		Х		Х	Х	Xi	
Adherence assessment			Х	Х	Х		
Quality of life and fatigue assessments		х		х	Х	Х	
Tumor measurement by imaging ^b	Х				Х	Xp	
Tumor markers (if applicable) ^c		Х		Х	Х		
CBC w/diff, platelets	Х	Х		Х	Х	Х	
Serum chemistries ^d	Х	Х		Х	Х	Х	
B-HCG ^e	Х						
INR check ^f			Х				
Phenolic levels (blood and urine)		Х		Х	Х		
Research labs (cytokines and growth factors)		Х		х	х		
Adverse event evaluation		Х	Х	Х	Х	Х	
Vital status ^g							Х

^a Pre-study imaging listed in table must be completed **within** 42 days prior to registration. Additional pre-study activities need not be repeated if performed within 10 days of starting study drug.

^b CT imaging or other imaging modality will be obtained at baseline (within 42 days of registration) and at 8 weeks (± 7 days). Imaging will then be q12 weeks (± 28 days) for as long as the patient remains on study. CT, PET/CT, or MRI are acceptable imaging modalities and all imaging will be considered per standard of care for patients on active cancer treatments.

^c Tumor-specific markers may include but are not limited to testosterone level and PSA for prostate cancer patients, CEA for colorectal patients, and CA19-9 for pancreatic cancer patients as performed per standard of care.

^d Albumin, alkaline phosphatase, total bilirubin, bicarbonate, BUN, calcium, chloride, creatinine, glucose, potassium, total protein, SGOT[AST], SGPT[ALT], sodium.

^e Serum pregnancy test (women of childbearing potential).

^f Patients taking warfarin will have INR checked within 2 weeks of starting MGE. This can be performed locally.

^g Vital status will be assessed by chart review or phone every 6 weeks (± 14 days) after patient comes off study.

^h Phone contact will occur 2 weeks after each clinic visit (± 3 days) until the Week 8 visit is complete. ⁱ Patients will not be asked to complete a pill diary after 6 cycles (24 weeks).

^jWeek 4 study appointments will be scheduled at day 28 ±3 days.

^k Study appointments at Week 8 and after will be scheduled 28 days after the prior appointment, ± 7 days

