6.2.2 Dose modification in the event of toxicity

In the event of dose-limiting toxicity, the patient will be removed from the study and the escalation decision rules defined above will be followed. There will be no dose-modifications on study. Either the patient or the treating physician can chose to discontinue MGE at any time. If necessary, MGE can be held for up to 7 days in the first month and for up to 21 days subsequently, as described in Section 6.5.1.

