6.5 Duration of Therapy

In the absence of treatment delays due to adverse events, treatment may continue until one of the following criteria applies:

- Disease progression, either by standard imaging or clinical parameters per the judgment of the treating physician,
- Intercurrent illness that prevents further administration of treatment,
- Unacceptable adverse event(s),
- Patient decides to withdraw from the study, or
- General or specific changes in the patient's condition render the patient unacceptable for further treatment in the judgment of the treating physician.

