6.6 Duration of Follow Up

Patients removed from the study for unacceptable adverse events will be followed until resolution or stabilization of the adverse event. Patients who are removed or withdraw from the study for any reason other than toxicity will be followed for vital status only after the 24 hour washout period. Patients will be followed every 6 ± 2 weeks until death for monitoring survival study endpoints.

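### No FACT-G or PROMIS-Fatigue score is tied to stopping MGE, so the Section 12.2.6 change estimates are likely to be too favourable unless dropout depends only on recorded scores

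*Combined protocol and SAP*

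**What the plan says.** **Schedule.** In the Section 6.1 table, the row "Quality of life and fatigue assessments" is marked at baseline, Week 4, Week 8 and every 4 weeks. It has no mark under Off-study, where the only entry is vital status: "Vital status will be assessed by chart review or phone every 6 weeks (± 14 days) after patient comes off study". The data-collection table for Section 11.0 agrees. It lists FACT-G and PROMIS-Fatigue at baseline and monthly, while the off-study documentation form and the best-response evaluation are listed at off-study.

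**Leaving.** Section 6.2.2: "In the event of dose-limiting toxicity, the patient will be removed from the study". Section 6.5 lists further reasons to end treatment, including "Disease progression, either by standard imaging or clinical parameters per the judgment of the treating physician", intercurrent illness and unacceptable adverse events.

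**After leaving.** Under Section 6.6, those who leave for any reason other than toxicity "will be followed for vital status only after the 24 hour washout period". For toxicity, "Patients removed from the study for unacceptable adverse events will be followed until resolution or stabilization of the adverse event". Neither rule mentions the questionnaires.

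**Analysis.** Section 12.2.6 plans a mixed model with time as a fixed effect and subject as a random effect, then: "We will use contrasts to estimate the changes from baseline to each follow-up time period". It gives no missing-data assumption, no sensitivity analysis and no rule for stopping or death. (It also names phenolic level as the outcome. The check here reads the model as meant for FACT-G and PROMIS-Fatigue.)

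**Inconsistency.** Section 6.3.2.2 has the research nurse "administer surveys at 4 and 8 weeks per protocol". Section 6.1, the data-collection table and Section 12.2.6 all have monthly collection.

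**The concern.** The events that end participation (toxicity, progression, worsening condition) are also events that would be expected to lower quality of life and increase fatigue. Patients have metastatic or unresectable disease, ECOG status up to 2 and a required life expectancy of only 3 months or more (Sections 3.1.1, 3.1.5 and 3.1.8), so early exits are foreseeable.

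If a patient deteriorates and stops between two visits, the last recorded score predates the deterioration, and nothing in the schedule obtains another. Each later contrast then rests on patients who tolerated MGE and had not progressed. A mixed model fills the gap by assuming that leavers would have followed stayers with similar recorded scores, which is doubtful when unrecorded deterioration is the reason for leaving. The report could then show stable quality of life on MGE while some patients declined on it. A score not taken at exit cannot be recovered later.

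**Working it through.** **The plan's own figures.** There is none to reproduce for this endpoint. The documents give no dropout rate, expected change, SD or power for FACT-G or PROMIS-Fatigue. The only sizing figure is the maximum of 30 (Section 12.3), which equals 5 dose levels × 6 patients. The bias does not depend on it.

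**Assumed inputs (none from the documents).** A scale on which higher is better; SD 15; within-patient correlation ρ = 0.6; stayers change by −1 at Week 4 and −2 at Week 8. A share d of patients (20%, 40% or 60%) leave after the Week 4 questionnaire and have no Week 8 questionnaire. Leavers are D points (0, 5 or 10) worse than stayers at exit. The true Week 8 change counts each leaver at that exit value. The model has a random intercept and categorical time.

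**Case A: the decline comes after the last questionnaire.** The recorded scores carry no sign of it, so the model estimates the stayers' change and bias = d × D. For d = 0.4 and D = 10, the true change is −2 − 4 = −6, the model gives −2, and the bias is +4.0.

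**Case B: the decline is already visible at Week 4.** Given the baseline and Week 4 scores, the model carries forward ρ/(1+ρ) = 0.6/1.6 = 0.375 of the Week 4 deficit. The bias left is d × D × (1 − 0.375) = d × D/1.6. For d = 0.4 and D = 10, this is 4/1.6 = +2.5.

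**Case C: as Case A, but half of the leavers stop at the Week 8 visit and complete its questionnaire.** If a share f of leavers is recorded, the observed Week 8 mean includes f × d of them among 1 − d(1−f) patients. Hence bias = d × D × (1−d)(1−f) / [1 − d(1−f)]. For d = 0.4, D = 10 and f = 0.5, this is 4 × 0.6 × 0.5/0.8 = +1.5.

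Bias in the Week 8 change, in points (positive = too favourable):

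| d | D | A | B | C |
|---|---|---|---|---|
| 0.2 | 5 | +1.0 | +0.6 | +0.4 |
| 0.2 | 10 | +2.0 | +1.2 | +0.9 |
| 0.4 | 5 | +2.0 | +1.2 | +0.8 |
| 0.4 | 10 | +4.0 | +2.5 | +1.5 |
| 0.6 | 5 | +3.0 | +1.9 | +0.9 |
| 0.6 | 10 | +6.0 | +3.8 | +1.7 |

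Simulations of 400,000 patients per setting, fitted at the assumed variances, agreed with these formulas to within about 0.1 point.

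**Where the bias vanishes.** It is about 0 if D = 0, or if leaving depends only on the recorded Week 4 score. It is also 0 at Week 8 if every leaver's exit value is recorded and used there. Visits after the exit remain missing in any case.

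**The case against.** **A reader might infer that the estimate is certainly too favourable.** The documents do not support that. They contain no dropout rate and no scores, and a likelihood-based mixed model is unbiased when dropout depends only on recorded values. The direction is the expected one; the size is unknown.

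**A reader might also infer that most leavers go unrecorded.** That is not supported either. Several points at which a stop would be decided fall at or near a questionnaire visit: toxicity is assessed at 4 weeks (Section 6.2.1), first imaging is at 8 weeks ± 7 days (Section 7.0), and response is evaluated at the monthly clinic visit (data-collection table). A patient who stops there can complete that visit's forms under the present plan, and Case C shows how much this helps. Stops between visits remain possible, since Section 6.2.2 lets the patient or physician discontinue at any time and telephone contacts fall at Weeks 2 and 6. Their share cannot be known in advance.

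**The target may be on-treatment quality of life.** Objective 2.2.6 concerns patients taking MGE, so missing scores long after stopping are not in themselves an error. This stands, and Section 12.2.6 should say so. It does not close the gap: decline on MGE shortly before stopping belongs to that question and is what goes unrecorded.

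**Section 12.2.6 speaks of monitoring until the end of the study.** That could be read as collection after exit, but the vital-status-only rule in Section 6.6 contradicts that reading for patients leaving for reasons other than toxicity.

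**The stakes are modest.** This is one of seven secondary objectives in an uncontrolled study, and no decision rule uses it. Under the assumptions above, the SD of a within-patient change is 15 × √(2 × 0.4) = 13.4. With all 30 patients observed, the standard error is 13.4/√30 = 2.4 points, so a 4-point bias is about 1.6 standard errors. This limits the severity. Without a control arm, an exit score also cannot separate disease course from an effect of MGE.

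**Conclusion.** The concern holds as a gap in the plan with a likely, unproven bias. It is established from the documents that no quality of life or fatigue assessment is linked to stopping MGE, that toxicity and progression end participation, that follow-up after leaving does not provide for the questionnaires, and that Section 12.2.6 does not address informative dropout. The inconsistency between Section 6.3.2.2 and the monthly schedule is also established and needs no assumption.

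The contrasts are likely to be too favourable unless dropout depends only on recorded scores. Under the assumed inputs the Week 8 bias ranges from 0 to about 6 points, and the upper end requires 60% leaving, 10 points of extra decline and none of it recorded. The point merits correction because the remedy is cheap and the data are otherwise lost. It does not touch the primary objective: the MTD rests on DLTs alone.

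**What to change.** 1. **Section 6.1 and the data-collection table:** mark FACT-G and PROMIS-Fatigue once when MGE is stopped, in clinic or by telephone, unless they were completed at a scheduled visit that day.
2. **Section 6.6:** either complete the questionnaires within the 24-hour washout, or amend the vital-status-only rule to permit this one assessment.
3. **Section 12.2.6:** state that the target is change while taking MGE, up to stopping. Analyse the exit score at its actual time or in the nearest visit window. Report the number missing at each visit with reasons, and show the contrasts with and without exit scores. Name FACT-G and PROMIS-Fatigue as the outcomes in place of phenolic level.
4. **Section 6.3.2.2:** reconcile the Week 4 and Week 8 surveys with the monthly schedule in Section 6.1, the data-collection table and Section 12.2.6.

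**Cost:** one short extra questionnaire set per leaver, with some refusals among patients who are unwell. An exit score does not supply the visits after stopping, which is why the target has to be stated.

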At the time of sacrifice, various organs (heart, lung, liver, kidney, spleen and brain) were removed and weighed and the organ weights of mice treated with each dose of MGE were compared to the untreated control group. A portion of each organ was fixed in formalin, sectioned and stained with H & E. for assessment by a veterinary pathologist. In addition. the heart and kidney were assessed by echocardiography and radioimmunoassay of urinary proteins, respectively, as a further measure of heart and renal function. There was no difference in the weight or structure of the hearts of mice treated with increasing doses of MGE. Cardiac parameters including ejection fraction, fractional shortening, cardiac output, stroke volume and heart rate were all similar in mice treated with MGE compared to untreated Control mice. There was no difference in the weight or structure of the lungs of mice treated with MGE compared to the untreated control mice. The weight of the livers of mice treated with the two lowest MGE (0.25 and 0.5 mg phenolics/mouse/day) and the highest MGE (2.0 mg phenolics/mouse/day) concentrations were no different than the weight of the livers of the untreated mice. However, the weight of the livers of mice in the 1.0 mg phenolics/mouse/day) were slightly increased compared to the control. Spleen weight of mice treated with MGE was not significantly different than untreated control mice and the spleens of mice were generally within normal limits with one mouse in the highest MGE treatment group having some extra medullary hematopoiesis. The weight of the brains of mice treated with MGE was not significantly different than untreated mice. The brains were subdivided into four regions—cortex, cerebellum, hypothalamus and brainstem. All brain regions examined were within normal limits.

Conclusions from toxicity studies and corresponding clinical doses:

Little toxicity was observed at any of the doses tested. Therefore, the level of phenolics used to treat the mice suggests that this level of phenolics and corresponding numbers of capsules will likely be tolerated by patients. However, based upon patient compliance, a recommended dose range for patients would include 2, 4, 6, 8 and 10 capsules/day (corresponding to approximately 5, 9, 14, 18 and 23 mg phenolics/kg/day).

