6.3 Study procedures

6.3.1 Recruitment

- 6.3.1.1 Potentially eligible patients will be recruited from the Wake Forest Comprehensive Cancer Center
- 6.3.1.2 The research nurse (RN) will be contacted to review eligibility and to consent eligible patients in person.
- 6.3.1.3 The RN will obtain baseline surveys, clinical information and ensure research labs are drawn and processed per protocol. Pill dairy will be provided at each visit.
- 6.3.1.4 Study drug (30-day supply) will be provided to participant by the RN.

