$$\frac{(Dose \ Level \ \times \ 7 \ \times \ 4)_i - Pill \ Count_i}{(Dose \ Level \ \times \ 7 \ \times \ 4)_i}$$

In the formula above, pill count will be calculated from counting the number of pills returned as well as by summarizing the patient's pill diary. The percent of pills taken will be summarized by dose level using the mean and 95% confidence interval.

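### The adherence formula omits the twice-daily factor, the 30-day supply and the actual visit interval: at day 28, full adherence scores 85.7% and half adherence −14.3%

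*Combined protocol and SAP*

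**What the plan says.** Section 12.2.7 is the whole analysis of objective 2.2.7: "we will summarize the percent of pills taken at the end of every 4 week period i using the formula" (Dose Level × 7 × 4 − Pill Count) / (Dose Level × 7 × 4), evaluated for each period. On the one measured input, "pill count will be calculated from counting the number of pills returned as well as by summarizing" the patient's diary. The result is then summarised by dose level as a mean with a 95% confidence interval.

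The quantities that the formula should reflect are set elsewhere in the same document:

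- **Dose.** The schedule in Section 6.2 defines Levels 1 to 5 as 1 to 5 pills twice daily. Section 1.2 gives the same range per day: "a recommended dose range for patients would include 2, 4, 6, 8 and 10 capsules/day".
- **Supply.** Section 6.3.1.4: "Study drug (30-day supply) will be provided to participant by the RN". At follow-up visits, Section 6.3.2.2 has the nurse "provide 30-day supply of MGE at prescribed dose level".
- **Visit interval.** In the footnotes to the Section 6.1 table, Week 4 falls at day 28 ± 3. After that, "Study appointments at Week 8 and after will be scheduled 28 days after the prior appointment", with a window of ± 7 days.
- **Records.** The accountability logs in Section 9.1 hold the quantity dispensed, the date dispensed and the quantity returned.

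**The concern.** The formula has no factor for doses per day, no term for the quantity dispensed, and no term for the days between visits. The first omission halves the denominator, so each missed pill counts double. The second treats the two spare days of supply as missed doses. The third makes the score depend on when the visit happens. Pill Count also has two sources and no rule for combining them. If diary pills taken were entered, the score would run backwards.

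At stake is the only planned analysis of a named secondary objective (2.2.7, outcome 5.2.7), which would report wrong and sometimes negative percentages. The figure also matters for reading the safety result. A patient becomes inevaluable for DLT only through about a week of consecutive missed doses (Sections 6.5.1.1 and 7.1), so scattered missed doses leave the patient in the cohort. Adherence by dose level helps a reader judge whether a clean high level reflects tolerability or pills not taken.

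**Working it through.** **Inputs.** Level k means k pills twice daily, or 2k per day (Section 6.2). Supply is 30 days, or 60k pills (Sections 6.3.1.4 and 6.3.2.2). The visit interval d is 25 to 31 days to Week 4 and 21 to 35 days afterwards (Section 6.1). I assume that Pill Count is pills returned, that every unused pill is returned and counted, and that each interval starts with one full 30-day supply.

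**Step 1: the denominator.** The formula's Dose Level × 28 gives 28, 56, 84, 112 and 140 pills for Levels 1 to 5. The prescribed amount is 2k × 28 = 56k, which is 56, 112, 168, 224 and 280. The formula's figure is exactly half at every level.

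**Step 2: the score.** With true adherence a over d days, pills taken per unit of k are T = min(60, 2·d·a), and pills returned are 60 − T. The reported score is

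(28 − (60 − T)) / 28 = (T − 32) / 28.

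The level k cancels, so the results are the same at all five levels.

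**Step 3: a visit at exactly day 28.**

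- a = 100%: T = 56, returned 4, score (28 − 4)/28 = 85.7%.
- a = 50%: T = 28, returned 32, score (28 − 32)/28 = −14.3%.
- a = 0: returned 60, score (28 − 60)/28 = −114.3%.
- The score is zero at T = 32, which is true adherence of 32/56 = 57.1%.

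**Step 4: other permitted visit days.** Reported score by true adherence:

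| Interval | 100% | 90% | 75% | 50% |
|---|---|---|---|---|
| 21 days | 35.7% | 20.7% | −1.8% | −39.3% |
| 25 days | 64.3% | 46.4% | 19.6% | −25.0% |
| 28 days | 85.7% | 65.7% | 35.7% | −14.3% |
| 31 days | 100%* | 85.0% | 51.8% | −3.6% |
| 35 days | 100%* | 100%* | 73.2% | 10.7% |

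*The supply has run out. The most a patient can take is 60/62 = 96.8% of the prescribed amount at 31 days and 60/70 = 85.7% at 35 days.

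In a cohort of three fully adherent patients, two seen at 28 days and one at 21, the reported mean is (85.7 + 85.7 + 35.7)/3 = 69.0%.

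**Step 5: a permitted hold.** Section 6.2.2 allows up to 7 days off drug in the first month. Taking every pill on the other 21 of 28 days gives T = 42 and 18 returned. The score is (28 − 18)/28 = 35.7%, against 42/56 = 75%.

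**Step 6: alternative readings.** If Dose Level meant pills per day, the denominator would be 56k and the score (T − 4)/56. Day 28 then gives 52/56 = 92.9% for full adherence and 24/56 = 42.9% for half, and a 21-day visit gives 38/56 = 67.9% for full adherence. If instead exactly 28 days' supply were dispensed, the literal formula at day 28 would report 100% as 100%, 75% as 50% and 50% as 0%. If diary pills taken were entered as Pill Count, full adherence at day 28 would score (28 − 56)/28 = −100%, or 0% on the pills-per-day reading.

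**The case against.** The strongest reply is that Dose Level must mean pills per day here, because multiplying it by 7 × 4 yields a number of pills only on that reading, and Section 1.2 lists the range in capsules per day. The twice-daily point would then fall away, and half adherence would score 42.9% rather than a negative figure. But the only definition of Dose Level is the level number in Section 6.2, and Section 12.2.7 itself goes on to summarise by dose level. Even on this reading full adherence scores 92.9% at day 28 and 67.9% at day 21, so the formula is still wrong.

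Several narrower points stand:

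- Half adherence is not negative at every permitted visit: at 35 days it scores +10.7%.
- The diary reversal is conditional. Subtracting Pill Count suggests that pills not taken are meant, and the diary form is not in the document. What is certain is that no rule combines the two sources.
- No escalation, DLT, evaluability or MTD rule uses this percentage, and the raw counts are kept, so nothing is lost irretrievably. Blood and urine phenolics at Weeks 4 and 8 also bear on exposure.
- If every interval were 28 days, the score would be a fixed linear function of true adherence (2a − 1.143), and the ranking of dose levels would survive. Intervals vary, however: full adherence at 21 days scores 35.7%, the same as 75% adherence at 28 days.
- Dividing by all days in the interval scores a permitted hold as pills not taken. The corrected definition has to say how it treats held days.

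**Conclusion.** The concern holds. The formula cannot return the correct percentage under the plan's own dosing, dispensing and visit schedule. Its denominator is half the prescribed amount at every level. At day 28 with a 30-day supply, true 100% is reported as 85.7% and true 50% as −14.3%. Across the permitted intervals, a patient who takes every available dose scores anywhere from 35.7% to 100%.

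These figures rest on Dose Level being the level number, Pill Count being pills returned, and all unused pills coming back. Dropping the first assumption shrinks the error without removing it. The effect is confined to a descriptive secondary endpoint and does not touch the MTD. Even so, this is the whole stated analysis of that objective, and it should be corrected before adherence is reported.

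**What to change.** Replace the formula in Section 12.2.7 with

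Percent taken = 100 × (pills dispensed − pills returned) / (2 × Dose Level × days from dispensing to the visit).

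At day 28 this gives (60 − 4)/56 = 100% and (60 − 32)/56 = 50%, as it should. Adding only the factor of 2 is not enough: it leaves 92.9% and 42.9%.

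The section should also:

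- report the diary measure separately, as 100 × diary pills taken / (2 × Dose Level × days), and note that diaries stop after 24 weeks (Section 6.1);
- say whether days on a permitted hold stay in the denominator, or give the result both ways;
- flag intervals longer than 30 days, where a shortfall may reflect supply rather than behaviour. The 30-day supply and the window of up to 35 days must be reconciled in the protocol.

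The cost is one formula and a few defining sentences. The logs already hold quantities dispensed and returned and the dispensing date. They list no return date, so the end of the interval comes from the visit date. No new data collection is needed.
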